Study Duration for Part A Excluding the Screening Period, Part A subjects will participate in the study for approximately 10 weeks (from Day 1 through the Part A Follow-up OE).

Study Duration for Part B Excluding the Screening Period, subjects will participate in Part B for approximately 24 weeks (from Day 1 through Week 24).

Study Duration for Part A/B Cohort 8 Excluding the Screening Period, subjects will participate in Part A/B Cohort 8 for approximately 24 weeks (from Day 1 through Week 24).

Study Design This is a Phase 3, 2-part, open-label study designed to evaluate the safety, PK, PD, and efficacy of ivacaftor in subjects with CF who are <24 months of age at treatment initiation (Day 1) and have an ivacaftor-responsive *CFTR* mutation on at least 1 allele. Part A is designed to evaluate the safety and PK of multiple-dose administration of ivacaftor in subjects <24 months of age over 4 days of dosing, and to confirm (or adjust if necessary) the doses for Part B. Part B is designed to evaluate the safety, PK, PD, and efficacy of ivacaftor in subjects <24 months of age over 24 weeks. Part A/B Cohort 8 is designed to evaluate the safety, PK, PD, and efficacy of ivacaftor in subjects with CF who are 1 to <4 months of age, ≥ 38 weeks gestation, weigh at least 3 kg at the time of treatment initiation (Day 1), and have an ivacaftor-responsive *CFTR* mutation (consistent with the approved mutations in the region) on at least 1 allele. Subjects will receive an initial low dose of ivacaftor (based on their Day 1 age and weight) and they will continue that dose up to Day 15, at which time the dose may be adjusted to better match the median adult exposure. Subjects are intended to remain on that dose until they are 4 months of age and at least 5 kg, after which the recommended age- and weight-appropriate dose(s) will be administered.

Part A:

Subjects will be enrolled in Part A sequentially in the following cohorts:

- **Cohort 1:** subjects aged 12 to <24 months
- **Cohort 2:** subjects aged 6 to <12 months
- **Cohort 3:** subjects aged 3 to <6 months

Enrollment in Part A will begin with subjects in Cohort 1. Enrollment for subjects in Cohort 2 will begin after an assessment of safety and PK data for subjects from Cohort 1. Enrollment for subjects in Cohort 3 will begin after an assessment of safety and PK data for subjects in Cohort 2.

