 - Subjects will receive an initial low dose of ivacaftor (5.7 mg q12h or 11.4 mg q12h based on their Day 1 age and weight) from Day 1 up to Day 15, as follows:

Age	Weight Range	Starting Dose
1 month	≥ 3 kg	5.7 mg q12h
2 months	≥ 3 to <5 kg	5.7 mg q12h
2 months	≥ 5 kg	11.4 mg q12h
3 months	≥ 5 kg	11.4 mg q12h

All subjects must have gestational age ≥ 38 weeks and weigh ≥ 3 kg.
Subjects 3 months of age must weigh ≥ 5 kg on Day 1.

- Study visits will occur on Days 1, 4, and 15.
- Follow-up Telephone Call (Day 1 evening)
- PK samples will be collected before the morning dose on Day 4, between 2 to 4 hours and between 6 to 8 hours after the Day 4 morning dose.
- The subject's Day 4 PK data will be used to calculate exposure to determine a dose that is expected to bring the exposure for the subject closest to the adult median. This potential dose adjustment will be communicated in writing to the principal investigator for administration to the subject on Day 15.
- At the Day 15 Visit, a trough PK sample will be collected before the morning dose. The ivacaftor dose will be adjusted if necessary, to either 5.7, 11.4, 17.1, 22.8, or 25 mg, and the adjusted dose will be administered q12h starting with the evening dose on Day 15.
- Subsequent Treatment Period (Day 16 to Week 24):

- Follow-up Telephone Call (Day 17)
- Study visits will occur on Weeks 4, 8, 12, 18, and 24.
- The subject is intended to remain on the same dose from Day 15 until the subject is 4 months of age and at least 5 kg, after which the recommended age- and weight-appropriate dose(s) will be administered.
- PK samples will be collected before the morning dose on Week 8, between 2 to 4 hours and between 6 to 8 hours after the Week 8 morning dose.
- Additional PK samples will be collected before the morning dose on the Week 4, 12, 18, and 24 Visits to characterize the longitudinal PK profile.
- The entire treatment period of the study will be 24 weeks, after which subjects will be eligible to enroll in an Extension Study.
- Subjects who do not enroll in the Extension Study will have a Follow-up Visit within 4 weeks \pm 7 days after the last dose of study drug and a Follow-up OE within 12 weeks \pm 14 days after the last dose of study drug.

[figure not shown]

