^l Study drug will be administered q12h for 3 days and the last dose of study drug in Part A will be the morning dose on Day 4. The Day 1 and Day 4 morning doses will be administered in the clinic. Doses administered from the evening dose on Day 1 through the evening dose on Day 3 will be administered q12h at home. Each dose of granules will be mixed with approximately 1 teaspoon (5 mL) of appropriate liquid or soft food (as listed in the study manual). Details

Table 3-1 Study VX15-770-124: Part A (Screening, Treatment, Early Termination of Treatment, and Follow-up Periods)

Event/Assessment	Screening Period	Treatment Period					Early Termination of Treatment Visit	Follow-up Telephone Call	Follow-up Ophthalmologic Examination
	Day -28 to Day -1	Day 1	Day 2	Day 3	Day 4	Day 5	Within 5 Days After Last Dose of Study Drug	Day 14 (± 2 Days)	8 Weeks (± 14 Days) After Last Dose of Study Drug
In-clinic observation for 4 hours after administration of the first dose of study drug		X							
Study drug dispensing		X							
Adverse events	Continuous from signing of ICF through the Follow-up Telephone Call (Day 14 ± 2 days; see Section 14.1.1.3)								Ocular adverse events only
Medications and procedures review	Continuous from 28 days before the Screening Visit through the Follow-up Telephone Call (Day 14 ± 2 days)								

CF: cystic fibrosis; *CFTR*: CF transmembrane conductance regulator gene; ECG: electrocardiogram; ETT: Early Termination of Treatment; ICF: informed consent form; OE: ophthalmologic examination; PK: pharmacokinetic; q12h: every 12 hours.

of dose preparation and dose administration will be provided in the study manual. The administration dates and times and whether doses were administered with food during the 3 days should be recorded in each subject’s dosing diary.

Table 3-2 Study VX15-770-124: Part B (Screening and Treatment Periods)

Event/Assessment	Screening Period	Treatment Period (Day 1 to Week 24)							
	Day -28 to Day -1	Day 1	Day 3	Week 2 (± 1 Day)	Week 4 (± 5 Days)	Week 8 (± 5 Days)	Week 12 (± 5 Days)	Week 18 (± 5 Days)	Week 24 ^a (± 5 Days)
Informed consent ^b	X								
Inclusion/exclusion criteria review	X	X							
Clinic visit	X	X		X	X	X	X	X	X
Telephone contact			X						
Demographics	X								
Medical history	X								
CFTR genotype ^c	X								
weight ^d	X	X		X	X	X	X	X	X
Physical examination ^e	X	X		X	X	X	X	X	X
Vital signs ^f	X	X		X	X	X	X	X	X
12-lead ECGs ^g	X				X		X		X
Ophthalmologic examinations ^h	X						X		X

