Adverse events	Continuous from signing ICF through the ETT (if required) and Follow-up Visit (see Section 14.1.1.3)		Ocular adverse events only
Medications and procedures review	Continuous from 28 days before the Screening Visit through the ETT and Follow-up Visit (if required; see Section 10.3.1)		

ECG: electrocardiogram; ETT: Early Termination of Treatment; ICF: informed consent form; OE: ophthalmologic examination; PK: pharmacokinetic.

Table 3-4 Study VX15-770-124: Part A/B Cohort 8 (Screening, Treatment, Early Termination of Treatment, and Follow-up Periods)

Event/Assessment	Screening Period	Treatment Period (Day 1 to Week 24)							Early Termination of Treatment Visit ^a	Follow-up Visit ^b	Follow-up Ophthalmologic Examination ^c
	Day -28 to Day -14	Day 1	Day 4	Day 15 (± 1 Day)	Day 17 (± 1 Day)	Week 4 (± 5 Days)	Week 8 (± 5 Days)	Weeks 12, 18, and 24 (± 5 Days)	As Soon as Possible After the Last Dose of Study Drug	4 Weeks (± 7 Days) After Last Dose of Study Drug	12 Weeks (± 14 Days) After Last Dose of Study Drug
Informed consent ^d	X										
Inclusion/exclusion criteria review	X	X									
Clinic visit/ Assessment contact	X	X	X	X		X	X	X	X	X	
Telephone contact		pm			X						
Demographics	X										
Medical history	X										
██████████ weight ^e	X	X	X	X		X	X	X	X	X	
Physical examination ^f	X	X	X	X		X	X	X	X	X	
Vital signs ^g	X	X	X	X		X	X	X	X	X	
12-lead ECGs ^h	X		X			X		X	X		
Ophthalmologic examinations ⁱ	X							X ^j	X		X
Serum chemistry ^k	X	X	X	X		X	X	X	X	X	
Hematology ^k	X			X		X		X	X	X	
PK blood collection ^l			X ^m	X		X	X ^l	X	X ⁿ		
Sweat chloride test ^o	X	X		X		X	X	X	X		
Study drug administration ^q		X	X	X		X	X	X			

-
- ^a Subjects who prematurely discontinue treatment before their last scheduled dose will be required to complete the ETT Visit as soon as possible after the last dose of study drug and the Follow-up Visit. All subjects who prematurely discontinue from study drug treatment in Part A/B Cohort 8 will be eligible to enroll in an observational arm of the Extension Study.
- ^b The Follow-up Visit is not required if the subject completes the Part A/B Cohort 8 treatment period and enrolls in the treatment arm of the Extension Study. For all other subjects, the Follow-up Visit is not required if the ETT Visit occurs 3 weeks or later after the last dose of study drug (ivacaftor) or in the event that the subject initiates treatment with commercially available ivacaftor within 3 weeks of the final scheduled treatment visit or ETT Visit.

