- ^c Subjects who prematurely discontinue ivacaftor treatment in Part A/B Cohort 8 and received at least 1 dose of ivacaftor treatment in Part A/B Cohort 8 will have a Follow-up OE 12 weeks after the last dose of study drug. Subjects enrolling into the Extension Study within 12 weeks after the last dose of study drug are not required to have the Follow-up OE (the OE will be performed in the Extension Study instead). Subjects who initiate treatment with commercially available ivacaftor within 3 weeks of the ETT Visit will not have the Follow-up OE.
- ^d Informed consent may be obtained before the Screening Visit and must be obtained before any screening assessment is performed.
- ^e [REDACTED] weight must be measured with the subject in a dry diaper or dry underclothes only (see Section 12.5.1 for details). [REDACTED] weight measurements will be made before the morning dose on Day 1.
- ^f Full physical examinations will occur at the Screening, Week 24, and Early Termination of Treatment (ETT) Visits; abbreviated physical examinations will occur at all other study visits.
- ^g Vital signs include blood pressure (systolic and diastolic), temperature, heart rate, respiration rate, and pulse oximetry. The subject should rest for at least 5 minutes, if possible, before having vital signs measured. Day 1 vital sign measurements will be collected before the morning dose. Temperature must be obtained by the same method throughout the study.
- ^h All 12-lead ECGs will be performed before the morning dose. The subject should rest for at least 5 minutes, if possible, before having the ECG performed. The ECG will be performed before any other procedures that may affect heart rate, such as blood draws.
- ⁱ The screening OE may be performed at any time from screening until before the first dose on Day 1. If an adequate slit-lamp examination cannot be conducted at screening, subjects will not be enrolled until an adequate repeat slit-lamp examination is completed (within 4 weeks of the Screening Period). Eligibility criteria regarding the ophthalmologic findings must be met prior to dosing.
- ^j OE to be performed at the Week 12 and Week 24 Visits.

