#### Treatment-emergent (TE) Period

For Part A the TE period will include the time period starting from the first dose date of the study drug to the Follow-up Telephone Call, or the last dose date + 28 days for subjects who do not have a Follow-up Telephone Call. The TE period will be used for safety analyses unless specified otherwise.

For the combined Part B and Part A/B Cohort 8 the TE period will include the time period starting from the first dose date of the study drug to the Follow-up Visit, or to the end of study date for subjects who roll over into the Extension Study and for whom the Follow-up Visit is not required. The last dose date + 28 days will be used as the TE period end date for subjects who do not have a Follow-up Visit or an end of study date. The TE period will be used for safety analyses unless specified otherwise.

**Unscheduled visits:** Unscheduled visit measurements will be included in analysis as follows:

- In scheduled visit windows per specified visit windowing rules (Combined Part B and Part A/B Cohort 8 only).
- In the derivation of baseline measurements.
- In the derivation of maximum/minimum on-treatment values and maximum/minimum change from baseline values for safety analyses.
- In individual subject data listings as appropriate.

**Visit windowing rules:** The analysis visit windows for protocol-defined visits are provided in Appendix D. The windows will be applied using the following rules for both scheduled and unscheduled visits. If no measurement is available within a visit window, the assessment will be considered missing for the visit. If there is more than one measurement available within the same visit window, the following rules will be used:

• For all safety parameters, if there are multiple measurements within a visit window, then 1) the record closest to the target day will be used, with the exception of the threshold analysis in which the worst record will be used; 2) if there are multiple records within the same distance of the target day, the latest record will be used; or 3) the Safety Follow-Up (SFU) visit will not be windowed; instead, the nominal visit will be used in relevant

analyses; 4) the Follow-Up OE visit will not be windowed; instead, the nominal visit will be used in relevant analyses.

- For all efficacy parameters, if there are multiple measurements within a visit window, the record at the scheduled visit will be used. Otherwise,

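### Part A: the SAP closes the treatment-emergent period at the Day 14 call, so ocular adverse events first dated at the Follow-up eye exam reach no AE summary table

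*SAP*

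**What the plan says.** **SAP.** Section 8.1 defines the Part A treatment-emergent (TE) period: "the TE period will include the time period starting from the first dose date of the study drug to the Follow-up Telephone Call". A subject without a call gets last dose + 28 days. There is no exception for ocular events. Section 8.4.1 bounds TEAEs by this period, restricts the AE summary tables to TEAEs, and defines a post-treatment AE class for combined Part B and Cohort 8 only. All AEs appear in a listing.

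**Protocol.** Section 14.1.1.3 stops general AE collection in Part A at Day 14 but exempts ocular AEs, which are collected from the call to the Follow-up OE. In the adverse-event row of Table 3-1, the entry under the Follow-up OE is "Ocular adverse events only". Section 9.1.3 gives this exam to every Part A subject. Section 13.5.5.1 runs TEAEs to the end of participation, qualified by the words as applicable, and the synopsis says that "Part A subjects will participate in the study for approximately 10 weeks (from Day 1 through the Part A Follow-up OE".

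**Part B and Cohort 8.** The synopsis says "subjects will participate in Part B for approximately 24 weeks (from Day 1 through Week 24" and "subjects will participate in Part A/B Cohort 8 for approximately 24 weeks (from Day 1 through Week 24". Section 14.1.1.3 collects ocular AEs to 24 weeks (Part B) and 12 weeks (Cohort 8) after the last dose.

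**The concern.** The SAP adopts the Day 14 cut-off for general AE collection but not the ocular exception that the protocol attaches to it. Table 3-1 schedules an OE only at screening and at the Follow-up OE; the Part A ETT Visit has none. So the one exam that could reveal a new ocular finding comes after the TE period has closed.

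Safety is a primary endpoint of Part A, and Protocol 13.5.5 names TEAEs as the key safety assessment. An ocular AE recorded because of that exam would be collected, left unclassified and seen only in listings. If the subject later entered Part B, an event that began before the first Part B dose would be pretreatment there and tabulated only if it worsened.

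**Working it through.** The plan states no figure for this, so the check is study-day arithmetic on the documents' own timings.

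**Inputs.** Call: Day 14 ± 2. Follow-up OE: last dose + 56 ± 14 days (Protocol Table 3-1 and 9.1.3.1; SAP Table 11-1). Last Part A dose: Day 4. Fallback TE end: last dose + 28 days (SAP 8.1).

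| | Last dose Day 4 | Dosing stopped after Day 1 |
|---|---|---|
| TE end, with call | 14 ± 2 = Days 12–16 | Days 12–16 |
| TE end, no call | 4 + 28 = Day 32 | 1 + 28 = Day 29 |
| Follow-up OE | 4 + 56 = Day 60 (46–74) | 1 + 56 = Day 57 (43–71) |
| Smallest gap after call | 46 − 16 = 30 days | 43 − 16 = 27 days |
| Smallest gap after fallback | 46 − 32 = 14 days | 43 − 29 = 14 days |

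Every in-window Follow-up OE lies outside the TE period under either rule: 15 of 15 subjects at the minimum Part A size. The synopsis and SAP 6.1 describe the exam as within 8 weeks. Read literally, that allows an earlier exam, so the gaps hold for the scheduled window only.

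**Effect of one such event on the TEAE tables** (Clopper-Pearson 95% CI):

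- All of Part A: 0/15 (0–21.8%) instead of 1/15 = 6.7% (0.2–31.9%).
- One cohort of 5: 0/5 (0–52.2%) instead of 1/5 = 20% (0.5–71.6%).

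**AE class.** SAP 8.4.1 has no post-treatment class for Part A. Appendix C tells the programmer to sort AEs into pretreatment, TEAE or post-treatment without limiting the last to Part B and Cohort 8. Appendix C acts only on missing or partial start dates; missing and some partial dates default to TEAE. It does not rescue a fully dated event.

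**Part B and Cohort 8, days after last dose.** The TE period generally ends at the Follow-up Visit, 28 ± 7 = 21–35.

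- Part B: OE at 168 ± 14 = 154–182. Gap 168 − 28 = 140 days, range 154 − 35 = 119 to 182 − 21 = 161.
- Cohort 8: OE at 84 ± 14 = 70–98. Gap 84 − 28 = 56 days, range 70 − 35 = 35 to 98 − 21 = 77.

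These late ocular AEs are listed but not tabulated. In Part B only early discontinuers who have the Follow-up OE are affected. The documents give no discontinuation rate; assuming 0–20%, that is 0–3 of 15 in Part B and 0–2 early discontinuers of 10 in Cohort 8.

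**The case against.** The case for leaving the SAP as it stands has four parts.

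1. **Participation is used loosely.** Protocol 13.5.2.3 and SAP 8.2.3 take Part A concomitant medication to the end of participation, although medication review stops at the call, and the as-applicable qualifier leaves the TEAE cut-off open. This weakens the link to Protocol 13.5.5.1. It does not touch the main point: Protocol 14.1.1.3 explicitly collects ocular AEs to the Follow-up OE, and the SAP tabulates none that begin after the call or the fallback date.
2. **The main ocular outcome is already summarised.** This stands. SAP 8.4.6 tabulates cataract and lens opacity by visit, and SAP 8.1 keeps the Follow-up OE as a nominal visit. A new opacity would be counted there, so 0/15 against 1/15 applies to the TEAE tables alone. That summary is not specified to carry severity, relationship or seriousness, and red reflex is only listed.
3. **Listings suffice at this size.** Largely fair: all AEs are listed, and SAEs also have their own listing. After screening the OE covers only lens and red reflex, so late non-lens events would come mainly from parent report. Those events would still have no summary at all.
4. **Events 42 to 70 days after a four-day course need not be treatment-emergent.** This is a reasonable view, and a reason to add a separate ocular table and leave the general TE window alone.

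**Conclusion.** The concern holds for Part A. A stated SAP rule, not a missing detail, keeps every fully dated ocular AE first dated at an in-window Follow-up OE out of the AE summary tables and leaves it without an AE class. The result rests on the 8 weeks ± 14 days schedule and on complete onset dates. The documents give no ocular AE rate, so 15 of 15 counts exams outside the window, not events lost.

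The practical loss is modest: tabulated severity, relationship and seriousness of late ocular AEs, and any summary of late non-lens ones. It should be fixed because safety is a primary endpoint and the repair is cheap.

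For Part B and Cohort 8 no conflict with Protocol 13.5.5.1 is shown, since the synopsis ends participation at Week 24; late ocular AEs there are simply untabulated. Subjects excused from the Follow-up OE are unaffected. Those with no Follow-up Visit but an end of study date can be read as having a TE period that runs to that date.

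Separately, the protocol is inconsistent on who has the Cohort 8 Follow-up OE. The synopsis and 9.1 say "Subjects who do not enroll in the Extension Study will have a Follow-up Visit within 4 weeks" and attach the exam to the same group. Table 3-4 footnote c and 9.1.3.1 tie it to early discontinuers: "Subjects who prematurely discontinue ivacaftor treatment in Part A/B Cohort 8 and received at least 1 dose". These passages must be reconciled.

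**What to change.** - Add one summary table of ocular AEs from first dose through the Follow-up OE, by part and cohort, with severity, relationship and seriousness. Leave the general TE window unchanged.
- Extend the post-treatment AE class in SAP 8.4.1 to Part A, so that it agrees with Appendix C.
- Flag events with onset after the start of commercial ivacaftor, where recorded. The flag will be incomplete: medication review ends at the Day 14 call in Part A, and Table 3-3 describes it for Part B as "Continuous from 28 days before the Screening Visit through the ETT and Follow-up Visit (if required; see Section 10.3.1", with a similar end in Cohort 8.
- For Part A only, an alternative is to end the TE period for ocular AEs at the Follow-up OE. This would also align the SAP with Protocol 13.5.5.1.

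The cost is SAP wording, one derivation flag and one table; no new AE data are needed. The drawback is that some late ocular events unrelated to study drug will be counted, in Part B up to 168 + 14 = 182 days after the last dose. The Part A change is worth making even if the table for Part B and Cohort 8 adds little.

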For Part A/B Cohort 8, subjects must have documented genotype test results reviewed and approved by the Vertex medical monitor prior to Day 1. Genotype testing is expected to be initiated prior to screening and results must be available prior to Day 1.

Instruction for collecting a sample for *CFTR* genotyping will be included in the Laboratory Manual.

Elevation of LFT Parameters:

Subjects with new treatment-emergent ALT or AST elevations of $>3 \times \text{ULN}$ must be followed closely, including repeat confirmatory testing performed by the central laboratory within 48 to 72 hours of the initial finding and subsequent close monitoring of ALT and AST levels, as clinically indicated. In addition, if ALT or AST are $>5 \times \text{ULN}$, repeat follow-up levels must be obtained within 7 ± 2 days and followed up 7 days later. All reasonable efforts should be made to repeat confirmatory analysis by the central laboratory. If, under exceptional circumstances, these blood samples must be drawn and/or analyzed at a local laboratory, approval must be first obtained from the Vertex medical monitor. Elevations in LFTs measured by the local laboratory must be reported immediately to the Vertex medical monitor, and the subject must have the tests repeated and sent to the central laboratory as soon as possible (ideally within 48 to 72 hours).

LFT Elevations Leading to Study Drug Interruption:

Study drug administration must be interrupted immediately, and the Vertex medical monitor must be notified if any of the following criteria is met:

- ALT or AST $>8 \times \text{ULN}$, or
- ALT or AST $>5 \times \text{ULN}$ for 2 weeks or more, or
- ALT or AST $>3 \times \text{ULN}$ in association with elevation of bilirubin $>2 \times \text{ULN}$ and/or clinical jaundice

Repeat testing should be performed within 48 to 72 hours to confirm the initial elevation.

A thorough investigation of potential causes should be conducted, and the subject should be followed closely for clinical progression.

If no convincing alternative etiology (e.g., concurrent infections) for the elevated transaminases is identified, regardless of whether ALT or AST levels have improved, the subject must be discontinued from the study in consultation with the Vertex medical monitor (Section 10.4). Subjects in whom treatment is discontinued for elevated transaminases should have their transaminases monitored closely until levels normalize or return to baseline.

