#### 8.4.2 Clinical Laboratory

For treatment-emergent laboratory measurements, the raw values and change from baseline values of the continuous hematology and chemistry results will be summarized in SI units by visit.

For all LFT results, the maximum on-treatment LFTs will be summarized.

In addition, a listing containing individual subject hematology and chemistry values outside the normal reference ranges will be provided. This listing will include data from both scheduled and unscheduled visits.

Clinically significant abnormal findings will be reported as AEs.

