# Appendix D: Analysis Visit Window Mapping Rules for Safety and Efficacy Assessments

**Table 11-4 Analysis Visit Windows for Safety Assessments for Part B** 

Safety Assessment	Visit a	Target Study Day	Analysis Visit Window (in study days)
Serum Chemistry	Baseline	1	≤1
	Week 2	14	[2,35]
	Week 8	56	[36,70]
	Week 12	84	[71,105]
	Week 18	126	[106,147]
	Week 24	168	[148, Date of Week 24 Visit]
	Follow-up Visit	NA	Use nominal visit
LFTs	Baseline	1	≤1
	Week 2	14	[2,21]
	Week 4	28	[22,42]
	Week 8	56	[43,70]
	Week 12	84	[71,105]
	Week 18	126	[106,147]
	Week 24	168	[148, Date of Week 24 Visit]
	Follow-up Visit	NA	Use nominal visit
Hematology	Baseline	1	≤1
	Week 4	28	[2,42]
	Week 8	56	[43,70]
	Week 12	84	[71,105]
	Week 18	126	[106,147]
	Week 24	168	[148, Date of Week 24 Visit]
	Follow-up Visit	NA	Use nominal visit
Standard 12-Lead ECG	Baseline	1	≤1
	Week 4	28	[2,56]
	Week 12	84	[57,126]
	Week 24	168	[127, Date of Week 24 Visit]
Vital Signs	Baseline	1	≤1

	Week 2	14	[2,21]
	Week 4	28	[22,42]
	Week 8	56	[43,70]
	Week 12	84	[71,105]
	Week 18	126	[106,147]
	Week 24	168	[148, Date of Week 24 Visit]
	Follow-up Visit	NA	Use nominal visit
Ophthalmologic Exam	Baseline	1	≤1
	Week 12	84	[2,126]
	Week 24	168	[127, Date of Week 24 Visit]
	Follow-up OE visit	NA	Use nominal visit

When a subject is lost to follow up and last dose date is unknown, impute last dose date of all study drugs as last on-treatment visit date.

<sup>aVisit name is used to report data in tables, listings and figures.

Table 11-5 Analysis Visit Windows for Efficacy Assessments for Part B

Safety Assessment	Visit a	Target Study Day	Analysis Visit Window (in study days)
	Follow-up Visit	NA	Use nominal visit
weat Chloride	Baseline	1	≤1
	Week 2	14	[2,49]
	Week 12	84	[50,126]
	Week 24	168	[127, Date of Week 24 Visit]

When a subject is lost to follow up and last dose date is unknown, impute last dose date of all study drugs as last on-treatment visit date.

aVisit name is used to report data in tables, listings and figures.

Table 11-6 Analysis Visit Windows for Safety Assessments for Part A/B Cohort 8

Safety Assessment	Visit a	Target Study Day	Analysis Visit Window (in study days)	
Serum Chemistry	Baseline	1	≤1	
	Day 4	4	[2,9]	
	Day 15	15	[10,21]	
	Week 4	28	[22,42]	
	Week 8	56	[43,70]	
	Week 12	84	[71,105]	
	Week 18	126	[106,147]	
	Week 24	168	[148, Date of Week 24 Visit]	
	Follow-up Visit	NA	Use nominal visit	
Hematology	Baseline	1	≤1	

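### The SAP's closest-to-target rule lets the mandatory ALT/AST retest replace the elevated scheduled value in the by-visit safety tables when a Week 4 to 18 visit was early

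*SAP*

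**What the plan says.** SAP 8.1 lists where unscheduled measurements enter the analysis. The first place is "In scheduled visit windows per specified visit windowing rules (Combined Part B and Part A/B Cohort 8 only", so Part A is outside the rule. For safety parameters, "if there are multiple measurements within a visit window, then 1) the record closest to the target day will be used". The only exception named is a threshold analysis, which takes the worst value in the window. Ties are settled by date: "if there are multiple records within the same distance of the target day, the latest record will be used".

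The next bullet of the same section orders the records differently for efficacy: "For all efficacy parameters, if there are multiple measurements within a visit window, the record at the scheduled visit will be used". Distance to the target day matters there only when the scheduled visit has no measurement.

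SAP 8.4.2 states that raw and change-from-baseline values of the laboratory parameters "will be summarized in SI units by visit". It also plans a summary of maximum on-treatment LFTs and a listing of out-of-range values from scheduled and unscheduled visits.

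Protocol 12.6.2 requires, for a new treatment-emergent ALT or AST above 3 x ULN, "repeat confirmatory testing performed by the central laboratory within 48 to 72 hours of the initial finding". The protocol's schedules allow ±5 days at Weeks 4 to 24, and ±1 day at Week 2 (Part B) and Day 15 (Cohort 8).

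**The concern.** The extra sample is not taken at random with respect to the first result. For transaminases, the protocol mandates a repeat only after a value above 3 x ULN. Under the safety rule, that repeat competes on equal terms with the scheduled draw for the place in the by-visit table, and it wins whenever it is closer to the target day or ties. Through this route, the record kept depends on the first result having been high.

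Safety is a primary endpoint in every part of the study, and the cohorts are small (minimum 5 in each Part B cohort, 6 in Cohort 8). One substituted value can visibly change a cohort's mean or maximum at a visit. The efficacy rule in the same section would prevent this, and the SAP gives no reason for treating safety differently.

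**Working it through.** The plan states no figure for this, so the check applies the rule to every permitted visit day.

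**Inputs**
- Selection rule: closest to target, later record on a tie (SAP 8.1).
- Target days 28, 56, 84 and 126 for Weeks 4, 8, 12 and 18. Windows [22,42], [43,70], [71,105] and [106,147], the same for Part B LFTs and Cohort 8 serum chemistry (SAP Appendix D).
- Visit allowance of ±5 days, giving 11 possible visit days (Protocol Tables 3-2 and 3-4).
- Retest r days after the draw. The protocol's 48 to 72 hours give r = 2 or 3 if the result is available on the day of the draw.

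**Formula.** Let d be the visit day minus the target day. The retest is chosen if |d + r| ≤ |d|, which means d ≤ −r/2. It then falls at most 5 days after target, so it is always in the same window as the scheduled record.

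**Weeks 4, 8, 12 and 18**

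| Retest, days after draw | Visit offsets at which the retest wins | Share of 11 days |
|---|---|---|
| 2 | −5 to −1 | 5/11 (45%) |
| 3 | −5 to −2 | 4/11 (36%) |
| 4 | −5 to −2 | 4/11 (36%) |
| 5 or 6 | −5 to −3 | 3/11 (27%) |
| 7 | −5 to −4 | 2/11 (18%) |

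The rows beyond 3 days matter because the 48 to 72 hours run from the finding, not from the draw, and samples go to a central laboratory. The documents give no turnaround. An assumed 1 to 4 days puts the retest 1 + 2 = 3 to 4 + 3 = 7 days after the draw.

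Example: Week 8 visit on Day 53, retest on Day 55, target Day 56. The distances are 3 and 1 days, so the Week 8 row shows the retest.

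**Other visits**
- Week 2 (target 14) and Cohort 8 Day 15, ±1 day: only by a tie, with the visit 1 day early and the retest at 2 days. That is 1 of 3 days at r = 2 and 0 of 3 at r = 3.
- Cohort 8 Day 4: never, because a later sample is always further from the target.
- Week 24: never. The window is "148, Date of Week 24 Visit", so it closes on the visit date.
- A visit on or after its target day is never displaced by its own retest.

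**Sensitivity to day counting.** If sites count Week n as Day 7n + 1, one day after the SAP target, the counts at Weeks 4 to 18 become 4/11 (r = 2) and 3/11 (r = 3), and the Week 2 tie disappears.

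**Illustration (assumed values).** One infant has ALT 4 x ULN with a retest of 2 x ULN, and the others are at 0.8 x ULN.
- n = 5: (4 × 0.8 + 4)/5 = 1.44 becomes (4 × 0.8 + 2)/5 = 1.04 x ULN.
- n = 10: (9 × 0.8 + 4)/10 = 1.12 becomes (9 × 0.8 + 2)/10 = 0.92 x ULN.
- Overall column, at least 15 + 6 = 21 infants: a shift of 2/21, about 0.1 x ULN.

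**With the scheduled record first**, the count is 0 of 11 at every visit.

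**The case against.** The rule is explicit and prespecified, and it contradicts no other passage. Different rules for safety and efficacy are not in themselves an error. The peak is also well protected. Maximum on-treatment LFTs and maximum QTc are summarized, and unscheduled values feed the maximum and minimum derivations. Out-of-range values are listed from all visits, and clinically significant abnormalities become adverse events. Protocol 13.5.5 makes treatment-emergent adverse events the key safety assessment, and safety is descriptive without testing. All of this stands, and it limits what follows from the point.

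Four stronger readings are tempting, and the documents do not support them.

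- **That only abnormal values are replaced.** The rule ignores the value. Discretionary laboratory tests and weekly transaminases after resumption (Protocol 12.6.2), and unscheduled visits under the COVID-19 addendum, can displace a normal scheduled value. Values up to 3 x ULN have no mandated repeat, and a retest can be higher than the first result.
- **That the liver signal is lost.** It is retained in the outputs just listed.
- **That a value taken after interruption is mislabelled as on-treatment.** The by-visit tables cover treatment-emergent measurements, and that period is defined to run to the Follow-up Visit, so it includes time off drug.
- **That hematology, vital signs, other chemistry and ECG are affected in the same systematic way.** No retest is mandated for them. Repeat ECGs are discretionary, and if two same-day tracings are both recorded under the scheduled visit, a scheduled-first rule would not choose between them.

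The fractions rest on uniform attendance and are conditional on an elevation occurring, for which the documents give no frequency. The 5/11 figure needs a same-day result and the earliest permitted retest.

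**Conclusion.** The point holds in limited form. In Part B and Cohort 8, the safety rule can substitute the mandatory retest for the elevated ALT or AST that triggered it in the by-visit raw and change-from-baseline tables. This happens after an early visit at Weeks 4, 8, 12 or 18, or by a tie at Week 2 or Day 15. Given an elevation and uniform visit days, the chance is between 2/11 and 5/11, depending on how soon after the draw the retest is taken. Week 24, Cohort 8 Day 4 and Part A are not affected by this route.

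Because the mandated trigger is one-sided, the effect is a tendency to pull by-visit ALT/AST summaries down, most visibly in cohorts of 5 to 10 infants. It is record selection that depends on the result, in descriptive tables of a primary endpoint. This is a cheap improvement to make, not a defect that threatens the safety conclusions.

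**What to change.** In SAP 8.1, apply to by-visit safety summaries the order already written for efficacy. Where the window contains a record from the scheduled visit, use it. Only where that record is missing, use the unscheduled one closest to the target day, and the later of two at equal distance. Keep every scheduled and unscheduled record in the maximum/minimum, threshold and listing outputs, as now. Because SAP 8.4 names no threshold analysis, the same edit could say which tables the worst-record exception covers.

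The cost is a change of wording and one programming condition, with no new data. The downside is that some visit values lie up to 5 days further from the target day, still within the protocol's visit allowance. If the database is already locked, SAP Section 3 provides for documenting the change in the clinical study report.
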